Group leader adherence and competency. Therapist competence and adherence in delivering WCBT will be measured by independent ratings of session audiotapes, using the Therapist Adherence Scale for CBT for SocAD (89) that we adapted to fit the WCBT manual (TAS-WCBT; see Appendix). Training of independent raters will involve didactic review of the WCBT manual and the TAS, followed by rating 8 sessions from one of the Phase 1 pilot groups in discussion with Drs. [name], [name] and [name]. This will be followed by an assessment of inter-rater reliability based on ratings of a second pilot group (8 sessions). During Phase 2, integrity of WCBT and group leader drift will be addressed by rating 3 randomly selected sessions of each WCBT group. Drs. [name], [name] and [name] will give feedback to group leaders as necessary. Our R34 project yielded impressive TAS-WCBT session fidelity ratings. Trained independent raters rated 23 of 56 WCBT sessions, on 1-to-5 scales, ranging from 1 (ineffective discussion) to 5 (extremely effective discussion). The average overall rating across sessions was 4.23 (SD=.66). We expect adherence and competence to be further enhanced via technology-assisted delivery of WCBT (computer-assisted CBT in the CALM study yielded good to excellent competencies and adherence) (61).

Diagnostic interviewer training & inter-rater reliability. Two independent evaluators (IE) at each site will be trained to complete interviews (MINI, BPRS, & MSIF – see Table 2). They will be trained by Drs. [name], [name] and [name] via a 3-day training course during which they will conduct 5 or more interviews until inter-rater agreement on ratings and diagnosis is satisfactory (80% agreement). Then, each IE will be observed doing five or more interviews until there is 90% agreement for the MINI and 95% for the BPRS and MSIF. Throughout the study, 25% of participants will be randomly selected to repeat their assessment battery at one randomly selected time-point by a different IE. Spearman correlation coefficients will be calculated between each rater with coefficients above 0.85 deemed acceptable. If this standard is not obtained, further training will be provided. Using these interviews, the IE's ratings will again be compared to consensus ratings obtained via discussion between that IE and the PI's/Co-I until the 0.85 criterion is met.

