study assessments and encouraging participants to call our offices with questions and to report address/telephone changes. Assessment retention will also likely be enhanced by the newly developed work hours reporting method described below. Dates will be collected for all assessments, and those participants who schedule and complete an assessment within 75% of the time interval will be considered within protocol. Participants who do not schedule and complete an assessment within 75% of the time interval will be reported as deviating from protocol. Missed assessments will be tolerated, and there will be no dismissal from the study due to missed assessments. Research staff will continue participant contact attempts as their continued presence in the sample is needed for the proposed intent-to-treat analysis. Participants that have completed the study and have missed the 52 week follow up assessment time point will be contacted by the study coordinator by phone, email or mail. If the participant is interested in completing a follow up interview, this can be completed over the phone or face to face and the participant will be given a \$40 incentive for completing this interview.

MEASURES (see Table 4 for administration schedule)

Social anxiety disorder screening. As noted above, JVS consumers complete the MINI Social Phobia Inventory (MINI-SPIN; Connor et al., 2001) as part of their routine intake assessments at JVS. The MINI-SPIN is a three question measure that yields a total score ranging from 0-12. Nearly 90% of persons scoring five or greater on this instrument have been found to meet structured diagnostic interview criteria for generalized social anxiety (Connor et al., 2001).

Diagnostic interviews. Diagnostic assessments will be conducted for DSM-V disorders at baseline, post-treatment, and at 12, 26, and 52 weeks follow-up. The primary measure will be the MiNi International Neuropsychiatric Interview v. 7 (MINI; Sheehan et al., 2015). The MINI will be administered by Research Associates blinded to treatment conditions. The MINI is a widely used structured interview with excellent test-retest and interrater reliability (93, 94).

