Procedural consistency: 1.) *Recruitment and attrition.* Standardized study description forms and screening instruments will be used across sites. Refusal rates, attrition rates and reasons will be monitored and compared across sites 4 times a year with procedural changes where appropriate to maximize participant retention equally across sites. 2.) *Screening and assessment.* We will use manualized procedures for each measure; assessors will undergo standardized training in the measures, and an observation certification check in which the assessors will be observed and rated on adherence to procedures by either [name] or [name]. Assessors must pass the adherence check before being certified. Adherence checks will be repeated once per year to minimize site or assessor drift. 3.) *Psychiatric diagnostic interviews.* We will hold quarterly joint teleconferences among interviewers and PIs from both sites to discuss diagnostic issues, and cross-site consistency checks, in which 5% of audio-taped interviews at each site will be randomly selected to be blindly rated by interviewers of the other site. Rates of agreement will be analyzed and significant disparities corrected through additional interviewer training and adherence monitoring. 4.) *Treatment delivery.* Technology-assisted training in WCBT will facilitate cross-site consistency. Weekly group supervision will combine therapists from both sites to facilitate cross-site consistency. In addition, half-day cross-site (videoconference) workshops every six months (years 1-4) will serve for recalibrations. 5.) *Data collection and analysis.* This area involves development of methods for ensuring that data collection instruments are programmed; data are properly collected; participants are tracked and monitored over the course of the study; data sets are documented and maintained; variables are created and documented; and main analyses are conducted. Rapid feedback to each site about missing or incorrect data is essential. The study coordinator at each site will schedule and coordinate assessments for all participants, and speak daily with staff about any problems and procedural changes. Study coordinators at the two sites will participate in biweekly conference calls with the PIs to address any data collection problems. During startup, we will develop programs for computer-assisted data entry. These programs will include range checks and logic checks to ensure accuracy and consistency of acquired data, as well as incorporating the logic of skip patterns in assessment instruments. On a daily basis, results will be backed up onto secure servers to be maintained at each site. Backups of the centralized database onto an external medium will be carried out after every update to ensure that no data will be lost in the process. Data will be transferred from the UCLA site to the U of Michigan site for analysis. If there is missing data from participants that have ended the study, the study coordinator will contact participants via email and/or phone to obtain the missing data. Study coordinators will use an oral or written script that will explain the purpose of contacting the participant.

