Removing Participants from the Protocol. Based on our experience, removal of participants from the protocol for clinical reasons is expected to be very rare, and established procedures are available to appropriately respond to various forms of clinical deterioration. There have been occasional instances in our clinic where adult patients receiving individual CBT for social anxiety have required inpatient hospitalization due to comorbidity, or suicidality, but these have been rare. Nonetheless, participants may be removed from the trial for the reasons listed below. In each case, participants will be consulted regarding potential removal. Final judgment for participant withdrawal will be made via consensus of the two PI's and the JVS group leaders. Effort will be made to continue assessment of any participants removed from the trial. Withdrawn participants will be referred for the best available treatment outside the research protocol.

Worsening severity. During the active intervention phase, participants who experience significant worsening of SocAD symptoms will be evaluated and removed from the trial if they evidence a significant worsening of symptoms based on the Social Anxiety Change Index that persists for four consecutive sessions. Worsening suicidality or comorbid conditions that are determined to compromise participant safety will also be grounds for participant removal. These concerns may come to our attention directly via the group leaders,

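### An evaluator who misses the 0.85 reliability check is re-certified against a consensus that includes that evaluator's own judgement, so the second check is easier than the first

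*Combined protocol and SAP*

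**What the plan says.** The section Diagnostic interviewer training & inter-rater reliability provides two evaluators per site for the MINI, BPRS and MSIF. During the trial, "25% of participants will be randomly selected to repeat their assessment battery at one randomly selected time-point by a different IE". The pass rule is: "Spearman correlation coefficients will be calculated between each rater with coefficients above 0.85 deemed acceptable". On failure, "If this standard is not obtained, further training will be provided". The evaluator's "ratings will again be compared to consensus ratings obtained via discussion between that IE and the" PIs or co-investigator, and this continues until 0.85 is reached.

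Three other places bear on this:

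- Diagnostic interviews (Measures): "The MINI will be administered by Research Associates blinded to treatment conditions".
- Removing Participants from the Protocol: "Final judgment for participant withdrawal will be made via consensus of the two" PIs and the JVS group leaders.
- Cross Site Consistency Plan, item 3 (psychiatric diagnostic interviews): "5% of audio-taped interviews at each site will be randomly selected to be blindly rated by interviewers of the other site".

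The documents do not say how the consensus is formed, how many investigators take part, whether ratings are locked before the discussion, or whether the arm is masked during it.

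**The concern.** The first check is independent: two evaluators assess the same participant separately. The re-check carries the same number, 0.85, but its comparator is partly made by the person being tested. A correlation between a rating and a composite that contains that rating is raised by the overlap alone. The wording also allows repeated attempts until the mark is reached. An evaluator could therefore be returned to rating at a level of independent agreement that the first check would have rejected.

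At stake is the quality of the evaluator-rated measures: the MINI diagnosis of social anxiety disorder at each follow-up, the BPRS and the MSIF work-performance ratings. With two evaluators per site, one might cover about half of a site's interviews. That share is an assumption, since the plan does not give the split.

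A second matter is blinding. The re-check brings interviewers who are meant to be blind into case discussion with investigators whose own blinding is not stated.

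**Working it through.** **Inputs.** The pass mark (Spearman above 0.85), the 25% repeat sample and the consensus comparator come from the section on interviewer training. Sample sizes (300; 96 in Detroit, 204 in Los Angeles) come from Participants and Recruitment. The five assessment points come from Diagnostic interviews. The 0.85 is a chosen criterion, so there is no derived figure to reproduce. The weights in the consensus, equal variances and normality are assumptions.

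**1. Overlap formula.** Let the consensus be the mean of k raters (the evaluator plus k−1 investigators) with common pairwise correlation r. The covariance of the evaluator with the mean, and the variance of the mean, both equal (1+(k−1)r)/k. Hence

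corr(evaluator, consensus) = sqrt((1+(k−1)r)/k).

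**2. Independent agreement that is enough for 0.85.** For bivariate normal ratings, Pearson = 2·sin(π·Spearman/6). A Spearman of .85 is a Pearson of .861, and .861² ≈ .7414. Solving for r gives r = (k × .7414 − 1)/(k−1), which is then converted back with Spearman = (6/π)·arcsin(r/2).

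| Consensus | r needed (Pearson) | Spearman scale |
|---|---|---|
| Evaluator + 1 investigator | (2 × .7414 − 1)/1 = .483 | .47 |
| Evaluator + 2 | (3 × .7414 − 1)/2 = .612 | .59 |
| Evaluator + 3 | (4 × .7414 − 1)/3 = .655 | .64 |
| Evaluator + 4 | (5 × .7414 − 1)/4 = .677 | .66 |

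**3. One evaluator, both comparators.** Take an evaluator with a pairwise Spearman of .60. Against a consensus that includes the evaluator, the expected correlation is about .89, .85 or .83 with one, two or three investigators. Against the same investigators without the evaluator it is about .60, .67 or .70, below 0.85 each time.

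**4. Dependence on weight.** With one investigator and weight w on the evaluator, the correlation is (w+(1−w)r)/sqrt(w²+(1−w)²+2w(1−w)r). On the Pearson scale, w = .5 reaches .85 at r = 2 × .85² − 1 = .445. With w = .25, r = .744 suffices: (.25+.75 × .744)/sqrt(.0625+.5625+.375 × .744) = .808/.951 = .85. As w approaches 0 the inflation vanishes.

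**5. Illustrative pass rates.** Simulated normal ratings, pairwise Pearson correlation .70, sample Spearman above .85. The sample sizes are 25% of 96 = 24 and 25% of 204 = 51.

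| Comparator | n = 24 | n = 51 |
|---|---|---|
| One independent rater | about 3% | about 0.4% |
| Evaluator + 1, equal weight | about 84% | about 95% |
| Evaluator + 2, equal weight | about 66% | about 77% |
| Evaluator + 3, equal weight | about 57% | about 64% |
| Evaluator at 25% weight, 1 investigator | about 26% | about 18% |
| Evaluator at 10% weight, 1 investigator | about 9% | about 2% |
| Two investigators, evaluator excluded | about 9% | about 3% |
| Three investigators, evaluator excluded | about 13% | about 6% |

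The figures 24 and 51 are whole-trial repeat totals per site. The size of a re-check is not stated and is probably smaller. At n = 10 the contrast narrows to about 14% for one independent rater against about 70% for evaluator plus one.

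**6. Blinding.** Blinding is stated for the interviewers only. Investigators hold the code that links JVS case-files to research records (confidentiality paragraph before D 6). They review WCBT participants' weekly severity data (Protection Against Risk). The PIs decide withdrawals with the group leaders. Repeat batteries number .25 × 300 = 75. If the time-point is drawn evenly from five, 75 × 4/5 = 60 fall after randomisation and 15 at baseline. Table 4 schedules no baseline MSIF, so every trial MSIF interview is post-randomisation.

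**The case against.** The strongest reply is that this is ordinary calibration. A low correlation between two evaluators does not show which one is off, and it also contains real change between the two interviews. Comparison with senior raters is a sensible way to find out. The investigators contribute to the consensus, so it is only partly circular, and if they dominate it the inflation is small. All of that stands. It supports consensus discussion as a training tool; it does not make the discussed rating an independent pass mark.

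Other controls exist. Evaluators meet agreement targets before starting, adherence checks are repeated yearly, and the blind cross-site rating covers 5% of interviews. The last is a real but partial backstop: it is described for diagnostic interviews only and is not the criterion for re-certification.

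The size is also open to challenge. The low end of the range and the highest pass rates need the evaluator to carry half the consensus. The normal model does not fit categorical MINI diagnoses. Both points are fair, so the figures show direction and plausible scale, not an estimate for this trial.

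A reader might infer three stronger things, none of which the documents support:

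- That the PIs are unblinded. This is a reasonable inference from their access and duties, but it is never stated, and nothing settles the co-investigator's status.
- That the discussion reveals the arm. It is not clear whether the interviews used are repeat trial interviews or retraining interviews. Baseline and non-trial interviews have no arm to reveal, and symptom ratings can be discussed without naming it. Case-files are also kept separate to protect interviewer blinding.
- That the primary results are threatened. The LSAS is listed as subject-report in Table 4, and paid work hours are reported by participants.

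**Conclusion.** The point holds on the text alone: the re-certification comparator contains the judgement of the evaluator being re-certified, and no other section excludes it or locks ratings first. The nominal 0.85 is therefore easier to reach than in the first check. Under an equal-weight consensus of the evaluator and one to four investigators, it corresponds to an independent Spearman agreement of about .47 to .66; with less weight on the evaluator the gap shrinks. These values rest on the assumed weights, equal variances and normality.

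Arm disclosure is possible if post-randomisation interviews are discussed, because no masking rule is stated; it is not demonstrated. The consequence is confined to the MINI, BPRS and MSIF. This is a worthwhile, inexpensive correction to a quality-control rule, not a flaw in the primary analysis.

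**What to change.** In Diagnostic interviewer training & inter-rater reliability, replace the consensus comparator. After retraining, require 0.85 against ratings that exclude the evaluator being re-certified and that another existing evaluator makes independently, before any discussion. The other site's interviewers rating the audio recording, as in the Cross Site Consistency Plan, would serve. Where an instrument is not recorded, use the other on-site evaluator.

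Keep consensus discussion for training only, with ratings locked beforehand. Limit it to baseline or non-trial interviews, or mask the arm. For the MSIF, which has no baseline administration in Table 4, only non-trial interviews or masking will do. State which interviews the re-check uses, and which PIs and co-investigators are blinded.

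The cost is a protocol wording change, some additional cross-site rating beyond the planned 5%, and possibly longer retraining because the check is harder to pass.

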Randomization. We will randomize each cohort of six to either WCBT or VAU, until 17 WCBT and 17 VAU groupings are completed at JVSLA and 8 WCBT and 8 VAU groupings are completed at JVSD. In our R34, there was a median wait time of 15 days from assessment to randomization and median wait times were identical for WCBT (2.14 weeks) and VAU (2.14 weeks). We will not reduce group size in response to a longer-than-expected wait. We will re-assess participants on key assessment measures immediately prior to randomization for those who wait beyond one week. In our R34, groups assembled every two to three weeks and the randomization scheme was acceptable (100% of qualified participants agreed to be randomized). Participants will receive \$20 for attending randomization meeting. This reimbursement is for travel and any meals missed during the meeting.

Selection and delivery of the control condition. The proposed study aims to test the effect of WCBT on social anxiety and employment outcomes among unemployed, job seekers with SocAD. A comparison to treatment as usual is considered to be the most appropriate comparison condition for an effectiveness study because evidence-based psychosocial treatments for social anxiety are currently not provided for most unemployed people with social anxiety disorder. Thus, comparison to vocational services as usual (VAU) best tests an effectiveness-based hypothesis that WCBT leads to improved outcomes for work-seeking persons with social anxiety as compared to services as usually delivered in a vocational rehabilitation setting.

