We will use the same MLM approach that we used in our R34 pilot to compare individuals assigned to WCBT vs. VAU. 3-level models will incorporate repeated measures on individuals nested within the 50 6-person groups randomly assigned to WCBT or VAU. HLM software will be used (115). Individual baseline scores on each outcome variable will be incorporated as level 2 covariates to increase the precision and statistical power of tests of the randomized intervention and reduce regression to the mean artifacts (116). Observations will be centered at a post-intervention or follow-up time point to provide a straightforward WCBT vs. VAU comparison on outcome level. Persistence of intervention effects will be assessed through WCBT vs. VAU comparisons on the level 2 slopes characterizing individual outcome trajectories through 52-week follow-up; quadratic or piecewise slope terms (117) will be included if needed to reflect acceleration or slowing of change over time. Power estimates for the planned MLM analyses were conducted using Optimal Design software (118). The entire sample of 300 individuals, nested within 50 groups, with 5 assessments over time, will provide power of .8 to detect (at 2-tailed $p < .05$) an intervention effect on intercept or slope of at least $d=0.34$; power estimates range from .7 to detect $d=.30$ to .9 to detect $d=.39$. Effect sizes in the R34 pilot ranged from .46 for hours worked to 1.36 for social avoidance; this suggests that power in this larger R01 will be adequate to detect condition differences on all outcomes, including employment. These estimates assume a minimum intraclass correlation (ICC) between groups of .01, which is larger than the ICCs observed in the R34 pilot. If the ICC for the R01 is found to be substantially higher at .03, the effect size detectable with power of .8 will rise only slightly, from $d= .34$ to $d=.36$.

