Aim 2. Evaluate whether improvements in social anxiety mediate the effect of WCBT upon employment related behaviors and outcomes. We hypothesize that reductions in social anxiety will lead to more employment related behaviors and greater employment success. In addition, it is hypothesized that specific reductions in social anxiety will better explain the effects of WCBT on employment compared with general improvements in depression and generalized anxiety. Multilevel SEM will assess whether reductions in social anxiety explain WCBT effects on subsequent employment (hours worked, job search activities, job search self-efficacy). This approach provides several advantages that are essential to testing mediation in this design. First, it accounts for nesting of individuals within randomized groups (119); it allows us to focus on change by using centering to disentangle between- and within-person effects (112); it lets us specify temporal order (i.e., change in social anxiety symptoms precedes change in employment related outcomes), and it accommodates latent variables (e.g., hours worked) (119). In addition, multilevel SEM provides ways to formally compare multiple alternative mediation paths (120), which will be essential to testing our hypothesis that reduction in social anxiety will better explain WCBT effects on employment than improvements in depression and generalized anxiety. Mplus software (121) will be used for these analyses due to its flexible estimation capabilities, use of bootstrap algorithms appropriate for testing indirect effects (122), and ability to test and compare specific mediation effects (123). Simulations conducted in MPlus and ProcClin (124) indicate that power can be expected to exceed .8 to detect significance at $p < .05$ an indirect effect in which the two component standardized direct effects a' (WCBT \rightarrow SocAD) and B' (SocAD \rightarrow employment-related outcome) are .20 or above, which is larger than the minimum a' and B' effects observed in the R34 pilot.

Aim 3. Explore moderators of the effects of WCBT, including site, race/ethnicity, education, prior work experience, psychiatric medication status and comorbid depression. Moderation will be tested by adding moderating variables to the MLM regression models testing mental health and employment outcome effects (Aim 1). Because groups are nested within site (16 sites at JVSD and 34 at JVSLA),

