site-level effect differences will be tested as level 3 interactions with condition; assuming overall average WCBT effects on a given outcome are $d=.5$ or above, power is estimated at .8 to detect a between-site effect difference of $d=.4$ or greater. Moderation by time-invariant individual characteristics (race/ethnicity, education, pre-intervention work experience) will be incorporated as cross-level interactions with condition and with condition and time, in order to test moderation of outcome change trajectory as well as level at a specific post-intervention timepoint. Because it is possible for several moderators to vary from assessment to assessment (e.g., psychiatric medication, depression diagnosis), it may be necessary to model their effects as time-varying covariates at level 1, in cross-level interaction with condition, depending on the observed levels of variability. It is not possible to know in advance how individual-level moderating variables will be distributed across the 50 randomized groups; therefore it is difficult to estimate power to test multilevel moderation of WCBT effects, and projections are necessarily tentative (125). However, assuming that a given dichotomous moderator (e.g., comorbid depression diagnosis) is present in at least 30% of the sample and is distributed relatively evenly across the 50 groups, power should exceed .8 to detect an interaction effect (i.e., between-persons difference in WCBT effect) as small as $d=.20$. Because the JVSD site is expected to have minimal variability on race/ethnicity, we plan to test moderation by this variable only among the 36 groups at the JVSLA site. Power to detect differences in WCBT effects among 3 types of participants – Hispanic (anticipated $n=49$), African-American ($n=59$), and White ($n=110$) – is estimated at .8 for interaction effects as small as $d=.30$.

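### The Aim 1 model names no site term although cohorts are randomised 1:1 within site; adding one costs one degree of freedom and protects power if the sites differ, chiefly for paid work hours

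*Combined protocol and SAP*

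**What the plan says.** All references are to the combined protocol and SAP.

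- **Allocation** (Procedures, Randomization). Cohorts of six are randomised "until 17 WCBT and 17 VAU groupings are completed at JVSLA and 8 WCBT and 8 VAU groupings are completed at JVSD".
- **Aim 1 model** (Power Analysis and Statistical Strategy, Aim 1). It has three levels: repeated measures, individuals and the 50 groups. The covariate statement is "Individual baseline scores on each outcome variable will be incorporated as level 2 covariates to increase the precision and statistical power of tests". No site level or site covariate is named.
- **Aim 1 comparisons.** For outcome level: "Observations will be centered at a post-intervention or follow-up time point to provide a straightforward WCBT vs. VAU comparison on outcome level". For persistence: "comparisons on the level 2 slopes characterizing individual outcome trajectories through 52-week follow-up".
- **Aim 1 power.** Power is .8 at d=.34, on the assumption of a "minimum intraclass correlation (ICC) between groups of .01, which is larger than the ICCs observed in the R34 pilot". With an ICC of .03 the detectable d is given as .36.
- **Aim 3.** Site is listed among the exploratory moderators: "Moderation will be tested by adding moderating variables to the MLM regression models testing mental health and employment outcome effects (Aim 1"). The nesting is acknowledged ("Because groups are nested within site (16 sites at JVSD and 34 at JVSLA"; the counts are of groups), and "site-level effect differences will be tested as level 3 interactions with condition".
- **General approach to quantitative analysis.** Variables that differ significantly between arms at baseline may be considered as covariates.

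**The concern.** Site is a factor that the allocation holds in balance, yet the main analysis does not use it. In a balanced design that does not bias the treatment estimate. It does mean that any outcome difference between Detroit and Los Angeles counts as noise between groups, so the standard error is too large and the test is conservative.

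Nothing else in the plan brings the term in. The baseline-imbalance rule cannot select site, because the quotas make site identical across arms. The Aim 3 site-moderation model would ordinarily carry a site main effect, but it is not the main comparison. Aim 1 reuses the pilot's modelling approach, but the documents tie that pilot to Detroit, so this does not imply a site term.

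Paid work hours, the primary work outcome under Measures of employment, are the most exposed. Participants must be unemployed at entry (Inclusion), and Table 4 starts the follow-up employment questionnaire at 12 weeks. No baseline hours score can therefore absorb a site difference. For the LSAS and the job-search measures the baseline score may absorb part of it.

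**Working it through.** **Inputs from the documents.** 50 groups of 6; 34 groups at JVSLA and 16 at JVSD, 1:1 within each; two-sided .05; ICC .01 (sensitivity .03); detectable d .34 (.36); smallest pilot effect .46, for hours worked.

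**Assumed input.** The site difference that remains after baseline adjustment, δ, in within-site SD units. The documents give none, so the range 0 to .5 is shown.

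**Step 1: reproduce the plan.** The variance of a group mean is v = ICC + (1−ICC)/6, which is .175 at ICC .01. The SE of the arm difference is √(4v/50) = √.014 = .1183. With a noncentral t on 48 df, power is .804 at d=.34, .700 at .30 and .898 at .39 (plan: .8, .7, .9). Detectable d at power .8 is .338, and .354 at ICC .03 (plan: .34, .36). The plan's figures reproduce without any separate site variance.

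**Step 2: site omitted.** The estimate is still normal with mean d and variance 4v/50. The residual sum of squares divided by v becomes noncentral chi-square on 48 df, with noncentrality λ = δ²(34×16/50)/v = 10.88δ²/v. With v=.175, λ is 5.6 at δ=.3 and 15.5 at δ=.5. The estimated SE, and so the confidence interval, widens by about √(1+λ/48): 6% at .3 SD and 15% at .5 SD.

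**Step 3: site included.** Noncentral t on 47 df; δ drops out.

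| | δ=0 | .2 | .3 | .4 | .5 | with site |
|---|---|---|---|---|---|---|
| Power, d=.34, ICC 0 | .82 | .81 | .79 | .76 | .73 | .82 |
| Power, d=.34, ICC .01 | .80 | .79 | .77 | .75 | .71 | .80 |
| Power, d=.34, ICC .03 | .77 | .75 | .73 | .71 | .68 | .77 |
| Power, d=.46, ICC .01 | .97 | .96 | .96 | .95 | .94 | .97 |
| Power, d=.46, ICC .03 | .95 | .95 | .94 | .93 | .92 | .95 |
| Type I error, ICC .01 | .050 | .045 | .039 | .032 | .025 | .050 |
| Detectable d, ICC .01 | .338 | .344 | .352 | .362 | .374 | .338 |

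Simulation of the 50 group means (200,000 replicates) agrees within about .002 at ICC .01. In a separate simulation the mean estimate at d=.34 is .339 to .341 in both models, so there is no bias. With the group variance constrained to be non-negative, as REML would do, power at ICC .01 runs from .790 (δ=0) to .710 (δ=.5) without site, against .788 to .793 with it.

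**Step 4: thresholds at ICC .01.** Detectable d passes the plan's .36 at δ of about .38. Power at .34 falls 5 points below the site-adjusted model at about .37.

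**Step 5: what baseline adjustment absorbs.** Suppose the same gap δ exists at baseline and follow-up, with correlation ρ (assumed). The residual gap is δ(1−ρ)/√(1−ρ²). For δ=.5 this is .29 at ρ=.5 and .21 at ρ=.7. For hours, with no informative baseline, the full .5 remains.

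**Step 6: slopes.** Person-level slopes over weeks 4, 12, 26 and 52 were simulated at d=.34 and ICC .01. A constant site shift of .5 SD leaves power at .805 in both models. A site difference in slope of .3 or .5 slope SD gives .78 or .71 without site, against .81 with it.

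**The case against.** The strongest reply is that no error is shown. The estimate is unbiased, type I error never exceeds .05, and the plan's power figures reproduce. The loss needs two things together: a residual site difference of about .4 SD or more and a true effect near .34, whereas the plan relies on pilot effects of .46 and above. A gap of .3 SD raises the total group ICC from .01 to about .029, inside the plan's own .03 case.

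The documents also give little reason to expect a large gap in hours. The Study Sites section describes very similar employment services, and unemployment is 9.1% v 9.7%. The contrasts that do exist are agency, screening or administrative figures, not trial data, and would have to work hard. Education (40% v 5% with a bachelor's degree) would alone need a graduate v non-graduate gap of .3/.35 = .86 SD to produce .3 SD, or .5/.35 = 1.43 SD to produce .5. The African American share (86% v 29%) would alone need .3/.57 = .53 or .5/.57 = .88 SD.

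Finally, the figures assume a normal outcome, while pilot hours clustered at 0 or 20 per week and the plan allows transformations, other link functions or a latent hours construct.

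All of this stands, and it limits the weight of the point. It does not show that site is in the Aim 1 model, or give a reason to leave it out. That hours are the most exposed outcome is a qualitative inference from the missing baseline; the calculations were not run on the actual distribution of hours.

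**Conclusion.** The point holds as an efficiency improvement of low to moderate priority. The Aim 1 outcome-level comparison leaves out a factor on which allocation is balanced, and no other rule in the plan supplies it.

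At d=.34 and ICC .01 the loss is about 1 point of power at a residual site difference of .2 SD, 3 points at .3 SD, 6 at .4 SD and 9 at .5 SD. At the pilot effect of .46 little is lost, at most about 3 points. If the sites do not differ, nothing is lost by omission and almost nothing by inclusion. The slope comparison is affected only if site changes trajectories.

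The size rests on an assumed site difference, on a normal outcome in SD units, and on the plan's own simplification of complete groups of six without attrition.

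**What to change.** - In the Aim 1 models, prespecify site as a fixed group-level (level 3) covariate on the intercept, and also on the slope where slopes are compared by condition.
- Carry the term into the Aim 2 and Aim 3 models that pool both sites. No power was calculated for these; the reason is consistency with Aim 1.
- In the Aim 3 site-moderation model, keep the site main effect alongside the interaction.
- Leave site out of the race/ethnicity moderation model restricted to JVSLA, where it is constant.

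The cost is SAP wording and, in the Aim 1 group-level comparison, one of 48 degrees of freedom. If the sites do not differ, power at d=.34 moves from .8039 to .8036 and detectable d from .3383 to .3385. No new data are needed. Fixing the term in advance also avoids a later, data-driven choice about adjusting for site.
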